1 ABBREVIATIONS AND DEFINITION OF TERMS

Abbreviation	Definition
ABR	auditory brainstem response
AE	adverse event
BSID-III	Bayley Scales of Infant Development, Third Edition
CS	clinically significant
CSF	cerebrospinal fluid
ECG	electrocardiogram
eCRF	electronic case report form
EOS	end of study
FDA	Food and Drug Administration
FPSS/TDS	Four Point Scoring System/Total Disability Score
GAG	glycosaminoglycan
HS	heparan sulfate
ICH	International Conference on Harmonization
IDDD	intrathecal drug delivery device
IT	intrathecal
KABC-II	Kaufman Assessment Battery for Children, Second Edition
LP	lumbar puncture
MedDRA	Medical Dictionary for Regulatory Activities
MPS	Mucopolysaccharidosis
MPS IIIA	Mucopolysaccharidosis IIIA or Sanfilippo syndrome Type A
MRI	magnetic resonance imaging
QoL	quality of life
Q4W	once per month
rhHNS	recombinant human heparan N-sulfatase
SAE	serious adverse event
SAP	Statistical Analysis Plan
Shire HGT	Shire Human Genetic Therapies, Inc.
US	United States
VABS-II	Vineland Adaptive Behavior Scales

2 INTRODUCTION

2.1 Background

This study, HGT-SAN-067, is an open-label, long term, multicenter, extension of Study HGT-SAN-055. The study is designed to evaluate the long-term safety, clinical activity, and biomarker outcomes of intrathecal (IT) administration of 3 dose levels (10 , 45 , and 90 mg once per month [Q4W]) of recombinant human heparan N-sulfatase (rhHNS, HGT-1410) via an intrathecal drug delivery device (IDDD) in subjects with Sanfilippo Syndrome Type A (MPS IIIA) who successfully complete the Phase I/II study HGT-SAN-055 (including end of study [EOS] assessments) and elect to continue to receive HGT-1410 treatment.

This statistical analysis plan (SAP) provides a technical and detailed elaboration of the planned statistical analyses for protocol HGT-SAN-067. Populations for analyses, data handling rules, statistical methods, and formats for data presentation are provided. The statistical analyses and summary tabulations described in this SAP will provide the basis for the results sections of the clinical study report (CSR).

The structure and content of this SAP provides sufficient detail to meet the requirements identified by the Food and Drug Administration (FDA) and International Conference on Harmonization (ICH) of Technical Requirements for Registration of Pharmaceuticals for Human Use.

This SAP is based on protocol HGT-SAN-067 Amendment 7, dated 08 February 2016. The reader of this SAP is encouraged to also read the clinical protocol for details on the conduct of this study and the operational aspects of clinical assessments and timing for completing a subject in this study

2.2 Study Rationale

This extension study (Study HGT-SAN-067) will evaluate the effects of long-term HGT-1410 administration on safety, clinical activity, and biomarker outcomes in subjects who completed Study HGT-SAN-055 and elected to continue therapy with HGT-1410.

3 STUDY OBJECTIVES

3.1 Primary Objective

[figure not shown]
- To collect long-term safety and tolerability data in subjects with Sanfilippo Syndrome Type A (MPS IIIA) who received HGT-1410 via a surgically implanted IDDD in study HGT-SAN-055 and elect to continue therapy in study HGT-SAN-067.

3.2 Secondary Objectives

The secondary objectives of this study are to:

- To collect, as measures of drug efficacy, over an extended treatment period (as change from baseline), the following: clinical, neurological, cognitive, behavioral, functional, and quality of life (QoL) assessments, together with potential imaging and biochemical biomarkers.

3.3 Exploratory Objective

- 

4 STUDY DESIGN

4.1 General Description

Study HGT-SAN-055 was a multicenter, multiple-dose, dose escalation study designed to evaluate the safety, tolerability, and clinical activity of up to 3 dose levels ([10, 45, and 90 mg] monthly for 6 months) of rhHNS administered via an IDDD in subjects with MPS IIIA. The study was planned to enroll up to 15 subjects to ensure a total of 12 subjects who completed the study (4 subjects per dose group). The primary objective was to determine the safety and tolerability of rhHNS via ascending doses administered via a surgically implanted IDDD once monthly for 6 months, in subjects with MPS IIIA. Safety was assessed through adverse events (AEs; types and severity), changes in clinical laboratory tests (serum chemistry, hematology and urinalysis), electrocardiograms (ECGs), cerebrospinal fluid (CSF) chemistries (including cell counts and inflammatory markers), and anti-rhHNS antibodies (CSF and serum). Secondary endpoints include the determination of the concentration of rhHNS in CSF and serum, and changes in CSF biomarkers. Additional secondary endpoints of potential efficacy included neurocognitive and developmental testing, quality of life measurements, and neurological assessments.

Long-term safety, clinical activity and biomarker outcomes of IT administration of rhHNS have been evaluated through the extension study, HGT-SAN-067. Subjects continued in the same treatment group they were assigned to in the HGT-SAN-055 study, with the exception of subjects in the 10 mg group who started transitioning in July 2013 to the 45 mg group following Protocol Amendment 4 (dated 03 May 2013). For all analyses under this SAP, subjects will be presented under the original treatment arm assigned in HGT-SAN-055. Analyses will be conducted on combined data from HGT-SAN-055 and HGT-SAN-067. In order to maintain a nomenclature system based on study chronology across the original HGT SAN-055 study and this extension study, the Baseline Visit for this extension study will be considered to be the day the subject received their first IT dose of HGT-1410 in Study HGT SAN 055.

The HGT-SAN-055 EOS assessment information provided the screening/start of study information for subjects who continued into the HGT-SAN-067 extension study. Once eligibility was confirmed, informed consent must have been obtained anytime from Week 20 in HGT-SAN-055 prior to performing any study-related procedures that were specific to HGT-SAN-067. This allowed subjects to have a nonfunctional IDDD replaced or revised prior to the first HGT-1410 dose in HGT SAN-067.

Enrolled subjects checked in to the study center 1 day before each of the scheduled HGT-1410 dosing days for safety assessments (designated Day 1). If no safety concerns existed, the subject subsequently received IT administration of HGT-1410 on Day 2 (± 2 days). However, if feasible and there were no safety concerns in the opinion of the investigator, the Day 1 and Day 2 assessments may have been combined and performed on Day 2; if this was done the results were to be recorded as Day 2. Subjects were to remain in the study center for at least 4 hours following dosing with HGT-1410 and were discharged from the unit when deemed clinically stable by the Investigator.

All subjects were to receive a series of standardized neurodevelopment assessments in the HGT-SAN-055 study. These assessments were to occur at Baseline and either prior to or at the 6-month time point. Subjects were to continue in HGT-SAN-067 with whichever age specific assessment they began in HGT-SAN-055. If, however, a subject's capability improves and they became capable of completing assessments at a higher level, such additional assessments may have been added. Any additional assessments were to be performed after the original assessments (those previously used in study HGT SAN-055) had been carried out. A magnetic resonance imaging (MRI) of the head and auditory brainstem response (ABR) testing were performed at Months 12, 24, 36, 54, 60, 72, 84, 96, 102 and EOS (only for MRI). X-rays may have been performed to investigate device malfunction, and to verify correct catheter and port placement following surgical implantation or revision. In addition, fluoroscopy should have been employed intraoperatively to guide catheter placement. Thus, subjects may have undergone 3 X ray examinations in association with each episode of IDDD malfunction and subsequent IDDD revision or replacement. Since the number of IDDD revisions/replacements was limited to 2 in any 6 month period (including the time in the HGT-SAN-055 study), the number of protocol associated X-ray evaluations was limited to 6 exposures in any 6 month period (including time in the HGT-SAN-055). Subjects were also to have X-ray examinations of the device performed at the EOS visit if the subject was to continue to receive intrathecal HGT-1410 beyond the end of the study.

Subjects were evaluated for safety throughout the study. Use of concomitant medications, therapies, and procedures were recorded and AEs were monitored. Adverse events that occurred in HGT SAN-055 and that were ongoing at enrollment in HGT-SAN-067 were to be captured in the case report forms (CRFs) for study HGT-SAN-067. For these ongoing AEs, the records from HGT-SAN-067 were reported and the records from HGT-SAN-055 were to be excluded. Specific safety stopping criteria were applied and were based on the types and severity of AEs reported while on study. These data were reviewed to inform the decision to discontinue a subject, a dose group, or the study as a whole.

All subjects were to have an EOS visit 30 (\pm 7) days following their last administration of HGT-1410 (ie, Month 102); however, this extension study was discontinued early as efficacy criteria were not met in the Phase IIb safety and efficacy study, HGT-SAN-093, and the study did not yield clinical proof-of-concept and all studies in the Sanfilippo Syndrome Type A program have been discontinued. The EOS procedures included standard clinical laboratory tests (serum chemistry, hematology, and urinalysis) in CSF and blood, protocol specific laboratory testing (eg, anti-rhHNS antibody testing), neurodevelopmental testing, ABR, child health questionnaires, MRI and an X-ray examination of the device.

All subjects were to be contacted by telephone or have a visit for a Final Safety Follow up, to be conducted at 30 (\pm 7) days after the EOS visit to collect updated information on AEs and concomitant medications, therapies, and procedures.

It is anticipated that the IDDD would be used to obtain CSF samples and to deliver administrations of HGT-1410. However, if a subject's IDDD appeared nonfunctional or if its use was precluded on a scheduled day of dosing, site personnel were to refer to the operations manual (for the PORT-A-CATH IDDD) or the IDDD Manual (for the SOPH-A-PORT Mini S

IDDD), which describes the investigation and management of IDDD-related issues. This included possible partial revision or complete replacement of the IDDD. As noted above, a maximum of 2 partial revisions and/or complete replacements could occur in any 6-month period. If revision or replacement of the IDDD could not be scheduled in time to avoid a delay of the next scheduled dose of HGT-1410, or if the subject experienced more than 2 IDDD malfunctions in a 6-month period (including participation in study HGT-SAN-055), HGT-1410 was to be administered via lumbar puncture (LP). Study drug may have been administered via LP for a maximum of 5 successive monthly doses, after which, IDDD re-implantation or revision must have occurred.

If there was no significant safety risk in the opinion of the Investigator, a non-functional IDDD may have been left in situ for up to 3 months.

In light of the higher than expected complications experienced with the PORT-A-CATH IDDD, the SOPH-A-PORT Mini S device was introduced for those subjects requiring replacement or revision. This device has design features anticipated to reduce complications encountered with the PORT-A-CATH IDDD device. Specific device assessments were included in the protocol to collect information with respect to information specific to SOPH-A-PORT Mini S device safety and function.

Subjects who discontinued or were withdrawn before receiving 3 monthly IT injections were not have to have undergone the EOS evaluations but were to have their IDDD removed.

In the protocol, it was planned that subjects were to have the IDDD removed when they discontinued from the study, unless the subject was continuing to receive treatment through another mechanism (eg, extension study, expanded access, commercially available). However, during study close out after the study was discontinued early, it was determined that some investigators would prefer to not remove the IDDD for some subjects unless a safety concern arises.

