4.3 Method of Assigning Subjects to Treatment Groups

All subjects enrolled in this extension study initially received doses of HGT-1410 Q4W via an IDDD at the same dose (10, 45, and 90 mg) as the group to which they were assigned in Study HGT-SAN-055:

- Group 1: HGT-1410 administered by IT injection 10 mg once per month (Q4W)
- Group 2: HGT-1410 administered by IT injection 45 mg once per month (Q4W)
- Group 3: HGT-1410 administered by IT injection 90 mg once per month (Q4W)

Subjects assigned to Group 1 had their dose increased to 45 mg Q4W at the first administration of HGT-1410 following full approval of Protocol Amendment 4.

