7.6.2 Kaufman Assessment Battery for Children II (KABC-II)

The Kaufman Assessment Battery for Children is an individually administered measure of the processing and reasoning abilities of children and adolescents between the ages of three and eighteen years. A detailed description of the KABC-II is provided in the KABC-II manual (Kaufman, 2004).

The KABC-II is an alternative to BSID-III. The KABC-II DQ scores, which are based on the average non-verbal age equivalent scores (see appendix I for additional details) will be combined with the BSID-III cognitive DQ scores and summarized at each assessment time point. The change from baseline at visits will be summarized as well. Similarly, the corresponding age-equivalent scores will be tabulated. Most of the subjects will have either only BSID-III data or KABC-II data. If a subject has data obtained by each of these methods, then the method for which data is available at both baseline and post-baseline time points will be used when combining the DQ scores and age-equivalent scores. KABC-II data will be presented in by-subject listings (3-6 years and 7-18 years).

Plots of mean BSID-III/KABC-II DQ scores across time will be presented. A spaghetti plot of DQ scores (and corresponding age-equivalent scores) of BSID-III/KABS-II against chronological age will be presented. On the graph the time when 10 mg subject switched to 45 mg will be indicated.

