7.7 Analysis of Biochemical Endpoints

7.7.1 Total Heparan Sulfate Levels

The observed values at each visit and the change from baseline to each of the post-baseline visits will be descriptively summarized for CSF total heparin sulfate levels by dose group. Heparin sulfate levels (CSF) will be presented in a by-subject listing.

Graphical plot of mean CSF total HS levels across time will be presented. In addition, a spaghetti plot of total heparin sulfate levels over time will be presented. The impact of positive serum anti-rhHNS antibody result will also be explored graphically using a spaghetti plot and/or individual subject plots. Urine GAG levels will be presented in a by-subject listing.

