7.9.1 Adverse Events

Aes will be recorded throughout the study and at early termination. Aes will be coded using the Medical Dictionary for Regulatory Activities (MedDRA) version 13.1 or higher.

Treatment-emergent Aes, defined as all Aes from the time of the surgery for first IDDD implantation in HGT-SAN-055 to the last day of reporting period (or cut-off date), will be summarized by treatment group. The summary will include the number and percentage of subjects with any AE, any drug-related AE, any surgery-related AE, any IDDD-related AE, any IT administration process-related AE, any severe AE, any serious AE (SAE), any serious drug related AE, and any AE that lead to discontinuation.

Treatment emergent Aes will be summarized by system organ class (SOC) and preferred term by dose group. The number and percentage of subjects experiencing an AE will be tabulated; recurrent Aes observed within a subject will be counted once. Furthermore, treatment-emergent Aes deemed as possibly/probably or definitely related to device surgical procedure, IDDD, investigational product, and IT administration process will be summarized separately. Treatment-emergent SAEs and treatment-emergent Aes which lead to study discontinuation will be similarly summarized.

By-subject listings will be provided for treatment-emergent Aes, treatment-emergent SAEs, deaths, and treatment-emergent Aes leading to discontinuation.

In general, an AE will be considered a treatment emergent AE if it cannot be definitively categorized by the available components (day, month, year) of the AE onset date with respect to the date of the IDDD implantation.

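### Tables that collapse time report events and end values arising at 45 mg under a 10 mg column, because Group 1 keeps its original label after the dose increase

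*SAP*

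**What the plan says.** Section 4.1 (General Description) sets the presentation rule: "For all analyses under this SAP, subjects will be presented under the original treatment arm assigned in HGT-SAN-055". It also pools the two studies: "Analyses will be conducted on combined data from HGT-SAN-055 and HGT-SAN-067". The same section makes an exception to continued dosing for "subjects in the 10 mg group who started transitioning in July 2013 to the 45 mg group following Protocol Amendment 4". Section 4.3 describes the change for the group as a whole: "Subjects assigned to Group 1 had their dose increased to 45 mg Q4W at the first administration of HGT-1410 following full approval" of Amendment 4.

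Sections 6.1 and 7 fix the columns as 10, 45 and 90 mg, and the result tables in Appendix II are by rhHNS dose group. For adverse events, Section 7.9.1 says: "Treatment emergent Aes will be summarized by system organ class (SOC) and preferred term by dose group". The event window there runs from the first device implantation in HGT-SAN-055 to the end of the reporting period. Sections 7.9.2 and 7.9.3 summarise laboratory and CSF chemistry values as change and shift from baseline to the end of the reporting period. CSF heparan sulfate is "descriptively summarized for CSF total heparin sulfate levels by dose group", visit by visit (Section 7.7.1).

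The switch is acknowledged in four places:
- the disposition table counts the subjects who switched (Section 7.1);
- the exposure summary gives the average dose actually received (Section 7.5);
- listings are sorted by dose group and then by dose (Section 7);
- the BSID-III/KABC-II spaghetti plot carries a marker, "On the graph the time when 10 mg subject switched to 45 mg will be indicated" (Section 7.6.2), and Section 7.6.3 plans the same for VABS-II.

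**The concern.** The primary objective is long-term safety, and the main safety tables have one column per original arm. After the dose increase, the 10 mg label no longer matches what Group 1 received. Someone reading a table in the study report, without the design section beside it, would take every event and end-of-period value in that column as experience at 10 mg. The study is open-label and non-randomised (Sections 4.2, 4.4 and 4.5), so there is no randomised comparison that would require the original label.

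At stake is whether the report can say what was observed at 10 mg and what was observed after the increase. For the tables that collapse time, it cannot.

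**Working it through.** The plan has no figure of its own to reproduce here. The check is a comparison of sections and some date arithmetic.

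**1. Which tables mix the doses.**
- *Adverse events (Section 7.9.1, Adverse Events).* There is one window per subject, not divided at the switch, and recurrent events count once per subject. An event that first occurs at 45 mg enters the 10 mg column. An event that occurs at both doses is counted once, with no sign of which dose came first. No subject-time is planned. With 4 completers planned per dose group (Section 4.1), one subject is 1/4 = 25 percentage points of a column.
- *Laboratory and CSF chemistry (Sections 7.9.2 and 7.9.3).* The tables use two time points, baseline and the end of the reporting period. For a Group 1 subject still on treatment at the end, the only post-baseline value is a 45 mg value. The by-subject listings in these sections cover the same two time points, plus values that became clinically significant after baseline. Sorting listings by dose therefore does not recover the last ordinary value at 10 mg.
- *By-visit summaries (DQ, VABS-II, FPSS, CSF heparan sulfate, MRI, antibody status).* Pre-switch values are genuine 10 mg data. Only post-switch values carry the wrong label. The switch followed approval of an amendment, not a fixed study month, so it may fall at different visits for different subjects.
- *Plots.* A switch marker is stated for the BSID-III/KABC-II and VABS-II spaghetti plots. None is stated for the heparan sulfate, MRI or antibody titre plots.

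**2. How long the label is wrong.** Inputs: start of the transition, July 2013 (Section 4.1); treatment-period cut-off, 30 January 2017 (addendum, Section 2). One month is 30.4375 days.
- From 1 July 2013: 1309 days / 30.4375 = 43.0 months (3.58 years).
- From 31 July 2013: 1279 / 30.4375 = 42.0 months (3.50 years).
- A subject who switched as late as 1 July 2014 (assumed): 944 / 30.4375 = 31.0 months (2.58 years).

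**3. What cannot be fixed from the document.** The start of 10 mg dosing is not given, so the share of Group 1 follow-up at 45 mg depends on an assumption. Take P months at 10 mg, 42.0 months at 45 mg and no withdrawals:

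share at 45 mg = 42.0 / (P + 42.0); mean dose = (10P + 45 × 42.0) / (P + 42.0)

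| P (assumed), months | Share at 45 mg | Time-weighted mean dose |
|---|---|---|
| 6 | 88% | 41 mg |
| 12 | 78% | 37 mg |
| 24 | 64% | 32 mg |
| 36 | 54% | 29 mg |
| 60 (total of 102 months, the last scheduled month) | 41% | 24 mg |

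The share runs from well over to below half, so these rows are illustrations only. The 42 to 43 months use dates in the document alone.

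**The case against.** The strongest reply is that this is a disclosed convention. Section 4.1 states the switch and the presentation rule together, so dose group means original cohort. The true average dose and the number switched are reported, and by-subject listings of at most 12 subjects carry much of the detail. Annotation of the remaining plots may also be left to figure shells. Much of this stands: the plan hides nothing, and it lowers the severity. It does not cure the tables, because none of these items separates safety results by the dose received.

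Three stronger readings are tempting, and the documents do not support them.
- *That the 10 mg event rate is inflated and any dose relation is pulled toward no difference.* This assumes that risk depends on dose. The documents do not show that, and the event summaries include surgery-, device- and procedure-related events. The SAP plans no dose comparison, test or model. Moving Group 1 time to the 45 mg column would add to its denominator as well as its numerator.
- *That no 10 mg column describes 10 mg.* Pre-switch values in the by-visit tables do.
- *That most of the Group 1 follow-up was at 45 mg.* This rests on an assumed time at 10 mg and on full retention.

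It is also fair to object to making a split by dose the main analysis. In Group 1, 45 mg always follows 10 mg, so dose cannot be separated from age, disease course, time with the device or cumulative exposure.

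**Conclusion.** The point holds for the tables that collapse time. Adverse events (including serious and related events) and end-of-period laboratory and CSF chemistry values arising at 45 mg will be reported as 10 mg. By-visit tables have a lesser problem: post-switch values keep the 10 mg label with nothing in the table to show it.

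The mislabelled period is up to about 3.5 years per subject. That takes July 2013 as the switch and assumes that the 30 January 2017 cut-off applies. The cut-off appears only in the addendum, which describes an interim-analysis SAP for Amendment 8; the main SAP is based on Amendment 7 and its text gives no cut-off. July 2013 is when the transition began. Individual switch dates and withdrawals are not given, so some subjects will contribute less.

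The mislabelling follows directly from the stated rules. Its effect on any impression of dose response, in size or direction, cannot be determined from the document. Severity: should-fix. The analysis is descriptive, but the change alters what the primary safety tables say. The addendum does not tabulate by dose group and is not affected.

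**What to change.** In the main SAP:
- Head the Group 1 column 10/45 mg in all tables, with a footnote giving the rule in Section 4.1.
- Keep the original-cohort tables. Add supplementary Group 1 tables of treatment-emergent, serious and related adverse events by dose at onset, with subject-years at each dose.
- Add the last value before the switch to the laboratory and CSF chemistry tables, beside the end-of-period value.
- Flag post-switch visits in the by-visit tables, and mark the switch on the heparan sulfate, MRI and antibody plots as is already planned for BSID-III/KABC-II and VABS-II.

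The cost is SAP wording and modest programming, since Section 7.5 already plans summaries and a listing of drug administration. The drawbacks are small cells, with about four subjects planned per group, and possible carry-over of 10 mg effects into the later period. Because dose and time are confounded within Group 1, the SAP should say that the split is descriptive and does not support a dose comparison.

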5.2 Primary Endpoints

The primary endpoints of this study were related to the long-term safety of intrathecal HGT-1410 administration. The safety endpoints were:

[figure not shown]
- AEs (type and severity)
- changes in clinical laboratory testing (serum chemistry including liver function tests, hematology, and urinalysis)
- electrocardiograms (ECG)
- CSF chemistries (including cell counts and inflammatory markers)
- anti-rhHNS antibodies (in CSF and serum).

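### AEs ongoing at rollover are reported from the HGT-SAN-067 record alone, with no rule that preserves the onset, worst severity or serious flag recorded in HGT-SAN-055

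*SAP*

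**What the plan says.** Four statements in the SAP bear on this point.

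- **Scope.** Section 4.1: "Analyses will be conducted on combined data from HGT-SAN-055 and HGT-SAN-067". Section 7.9.1 (Adverse Events) sets the treatment-emergent window as "from the time of the surgery for first IDDD implantation in HGT-SAN-055 to the last day of reporting period".
- **Endpoint.** Section 5.2 lists as a primary endpoint "AEs (type and severity)".
- **Handling of spanning events.** Section 4.1 says that AEs from HGT-SAN-055 that were "ongoing at enrollment in HGT-SAN-067 were to be captured in the case report forms (CRFs) for study HGT-SAN-067". It then adds: "For these ongoing AEs, the records from HGT-SAN-067 were reported and the records from HGT-SAN-055 were to be excluded".
- **Tabulation.** Section 7.9.1 counts subjects with AEs related to drug, surgery, device or the intrathecal administration process, and then "any severe AE, any serious AE (SAE), any serious drug related AE, and any AE that lead to discontinuation". It also states that "recurrent Aes observed within a subject will be counted once".

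Section 6.3 deals only with missing or partial AE dates. Appendix II plans a table by severity (10.3.1.3), but no rule says which grade a subject contributes when several are recorded.

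**The concern.** The reporting window opens in HGT-SAN-055, yet for one class of events the HGT-SAN-055 record is set aside completely. If such an event was severe or serious in the parent study and had eased by rollover, and if the extension CRF recorded its state from then on, the higher grade and the serious flag would not reach the primary safety tables. The event would still be counted, but as something milder.

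Rollover is a plausible time for such events. Section 4.1 allows consent from Week 20 of HGT-SAN-055 so that a nonfunctional device can be replaced or revised before the first extension dose. It also reports more complications than expected with the first device. Device and surgery AEs may therefore straddle the boundary. If the excluded record is also absent from the AE listings (12.2.7.1 and 12.2.7.2), a reader of the report could not detect a difference.

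**Working it through.** The SAP gives no figure to reproduce here. The check is a reading of every AE rule, followed by simple arithmetic.

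**1. Is there a carry-over rule?** Sections 4.1, 6.3 and 7.9.1 and Appendices II and IV contain none for onset, severity, seriousness or relatedness. The instruction to capture ongoing events in the extension CRF does not say which values are entered.

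**2. Is exclusion needed to avoid double counting?** Not in the subject-level tables. They count subjects, and repeated AEs within a subject count once, so a second record of the same event does not raise the incidence. The severity table does need a rule: with both records kept and no maximum-grade rule, one subject could appear under two grades. Merging to the maximum grade solves this; exclusion is not required.

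**3. Which outputs are exposed?** The severe, serious, serious drug-related and four relatedness rows of Table 10.3.1.1, and Tables 10.3.1.3 to 10.3.1.8. The any-AE row and the preferred-term counts keep the event through the HGT-SAN-067 record. Discontinuation rows are not exposed to HGT-SAN-055 discontinuations, because extension subjects completed that study. Dose-group assignment is unaffected, because subjects stay under their HGT-SAN-055 arm.

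**4. Illustration (attributes assumed).** One subject in a group of 4 has a single AE, recorded as severe, serious and related in HGT-SAN-055 and as mild, non-serious and unrelated in HGT-SAN-067.

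| Row | HGT-SAN-067 record only | Both records, subject counted once |
|---|---|---|
| Any AE | 1/4 = 25% | 1/4 = 25% |
| Severe | 0/4 = 0% | 1/4 = 25% |
| Serious | 0/4 = 0% | 1/4 = 25% |
| Related | 0/4 = 0% | 1/4 = 25% |

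**5. Size of one lost flag.** The SAP gives 12 planned completers, 4 per group, and an extension maximum of 12. The actual group sizes are not given, so a range is shown: 1/3 = 33.3 points, 1/4 = 25 points, 1/5 = 20 points. Overall it is 1/12 = 8.3 points. These apply only if the subject has no other AE that qualifies for the same row; otherwise the change is 0.

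**6. Direction.** Dropping one of two records can leave the worst grade or flag unchanged or lower it, never raise it. Onset is different. A pre-surgery event re-dated to rollover falls inside the window and would wrongly be added. A kept record with an erroneously early date would wrongly remove an event.

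**The case against.** The strongest reply is that the extension CRF captures the event that occurred in HGT-SAN-055, possibly in full with its onset and attributes, so that dropping the older copy only removes a duplicate. The treatment-emergent definition fits that reading, since it needs the true onset. CRF completion rules are also commonly kept outside a SAP. This part stands: the documents do not show that the kept record starts at enrolment, and no actual loss is demonstrated. It does not remove the point, because the exclusion itself is a stated SAP rule, is unconditional, and has no safeguard.

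A reader might infer three stronger things that the documents do not support:

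- **That severe or serious events are deleted.** The event stays in the counts; only its attributes are at risk.
- **That each lost flag costs 25 points.** Visits were planned to Month 102, so a subject may well have another qualifying AE, and the row would then not move.
- **That the bias always runs toward a milder profile.** That holds for severity, seriousness and relatedness against the worst value over both records, but not for onset.

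It is also fair to object that taking the strongest relationship from either record could override a later and better-informed causality judgement. That objection stands, and the fix respects it.

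**Conclusion.** The point holds as a gap in a stated record-selection rule. The SAP can lose primary-endpoint information for AEs ongoing at rollover, and the rule is not needed to prevent double counting of subjects. The size is zero if the two records agree. If they differ, each lost flag changes a dose-group row by 0 or 25 points and the overall row by 0 or 8.3 points, assuming 4 subjects per group and 12 in total. How many events span the studies, and how many of those differ, is not stated. The point should be settled before the tables are produced, but it is not evidence that the safety results are wrong.

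**What to change.** Replace the exclusion in section 4.1 with a merge rule, and repeat it in section 7.9.1:

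- Link the two records of each spanning AE and count the event once.
- Take the earliest onset date, the maximum severity, and serious if serious in either record.
- Take outcome and end date from HGT-SAN-067.
- For relatedness, keep the latest investigator assessment in the tables and flag every event where the records disagree.
- Show both source records in the listing.

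If the HGT-SAN-067 record already carries the first onset, worst grade and serious flag by CRF instruction, the SAP can say so instead, with a reconciliation of the two databases before lock.

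The cost is SAP wording, a small programming step on data already collected, and manual linkage of a few events in at most about 12 subjects. If the records already agree, no table changes.
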